9.2.1.1 Visit 1 – Screening visit

The screening visit should not take place more than 6 weeks prior to Visit 2 (start of treatment). If required, the data to be recorded at this visit may be collected over more than one day.

The following procedures will be performed and data recorded:

- Obtain written informed consent from the subjects/legal representative.
Note: No screening procedures can be performed unless written informed consent has been obtained.
- Eligibility check. No subject may start treatment with study drug until all inclusion and exclusion criteria are met as listed in Sections 6.1 and 6.2. Confirmation of selection criteria may be based on medical records for some conditions, but laboratory test results must be available for the listed items to confirm eligibility. For FVIII/FIX level and for inhibitor levels, subjects should not have received pre-assigned treatment within the times specified in Section 7.1.1, Table 7–2. In subjects whom screening laboratory does not confirm the severity of hemophilia (due to inadequate washout), the diagnosis must be supported by acceptable documentation.
- Demographic data: Year of birth, age at informed consent, sex, race and ethnicity (as allowed by local regulation), height, weight
- Medical history (see Section 9.3.2)
- Disease history (see Section 9.3.3)
- Medication history (see Section 9.3.4)
- Physical examination (see Section 9.6.3.2)
- Adverse events (see Section 9.6.1)
- Concomitant medications
- Vital signs (see Section 9.6.3.3)
- Blood samples for laboratory tests:
 - Complete blood count (CBC; see Section 9.6.3.1), platelets, serum chemistry (see Section 9.6.3.1)
 - FVIII/FIX level
 - FVIII/FIX inhibitor level.
Note: If a subject has a documented inhibitor positivity and is tested inhibitor negative at this visit, he is still eligible for enrolment as “subject with inhibitors”, provided he is on treatment with a bypassing agent.
 - Optional pharmacogenetic testing (PgX; see Section 9.3.5). Sample may be obtained at any point during the study once the separate informed consent form has been signed by the subject.
- Training on and dispense of EPD device
- Remind subject on wash-out from his pre-study product before next visit (see Table 7–2 in Section 7.1.1).

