9.6.1.1 Definitions

Definition of adverse event (AE)

In a clinical study, an AE is any untoward medical occurrence (i.e., any unfavorable and unintended sign [including abnormal laboratory findings], symptom or disease) in a subject or clinical investigation subject after providing written informed consent for participation in the study. Therefore, an AE may or may not be temporally or causally associated with the use of a medicinal (investigational) product.

In the following differentiation between medical history and AEs, the term “condition” may include abnormal (e.g., physical examination findings, symptoms, diseases, laboratory, ECG).

- Conditions that started before signing of informed consent and for which no symptoms or treatment are present until signing of informed consent are recorded as medical history (e.g., seasonal allergy without acute complaints).
- Conditions that started before signing of informed consent and for which symptoms or treatment are present after signing of informed consent, at *unchanged intensity*, are recorded as medical history (e.g., allergic pollinosis).
- Conditions that started or deteriorated after signing of informed consent will be documented as adverse events. This includes intercurrent illnesses

Definition of serious adverse event (SAE)

An SAE is classified as any untoward medical occurrence that, at any dose, meets any of the following criteria (a – f):

- a. Results in death
- b. Is life-threatening

The term ‘life-threatening’ in the definition refers to an event in which the subject was at risk of death at the time of the event, it does not refer to an event which hypothetically might have caused death if it were more severe.

- c. Requires inpatient hospitalization or prolongation of existing hospitalization

A hospitalization or prolongation of hospitalization will not be regarded as an SAE, if at least one of the following exceptions is met:

- The admission results in a hospital stay of less than 12 h
- The admission is pre-planned (e.g., elective or scheduled surgery arranged prior to the start of the study; admission is part of the study procedures as described in Section 9.2)
- The admission is not associated with an AE (e.g., social hospitalization for purposes of respite care).

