6.4 Safety

In accordance with the primary objective of the study, which is the assessment of the safety and tolerability of multiple subcutaneous doses of BAY 1093884 in subjects with hemophilia A or B with or without inhibitors, the primary variables of the study are the following:

- Incidences of drug-related AEs, SAEs, adverse events of special interest (AESIs), and clinically relevant abnormal laboratory values.

Hypersensitivity reactions, thromboembolic and thrombotic microangiopathic events are defined as AESIs.

In addition, the following safety variables are also of particular interest:

- Incidences of injection site reactions (ISRs)
- Incidences of binding and neutralizing antibodies against BAY 1093884

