6.4.1 Adverse events

The investigator has to record on the respective CRF pages all adverse events occurring in the period between the signing of the informed consent form and the end of the follow-up phase. The original terms used by investigators to report AEs via the CRFs will be coded using the Medical Dictionary for Regulatory Activities (MedDRA).

For each AE, the number and percentage of subjects who experienced at least 1 occurrence of the given event will be tabulated according to the affected primary system organ class (SOC) and preferred term (PT) by dose cohort and dose actually received. A total column will be included in all safety summaries.

Frequency tables, showing an overall summary of number of subjects with drug-related AEs, SAEs and AESIs will be given, and will include the following information:

- maximum intensity for any AE,
- AE related deaths,
- AE resulting in permanent discontinuation of study drug,

- treatment emergent AE.

AEs will be considered treatment-emergent if they begin after the first administration of study drug and they do not start after more than 30 days after the last administration. Determination of whether or not an event is treatment-emergent will be derived after the missing or incomplete AE start date is imputed. Inhibitors will be defined as treatment-emergent if they develop after first study drug application. Imputation rules for missing and incomplete AE start are described in section 4.3.

The severity or intensity of an AE should be graded according to the National Cancer Institute Common Terminology Criteria for Adverse Events (NCI CTCAE) version 5.0. If no exact matching code is available in NCI CTCAE version 5.0, the following guidance should be used:

- CTCAE grade 1: Mild
- CTCAE grade 2: Moderate
- CTCAE grade 3: Severe and/or disabling AE
- CTCAE grade 4: life-threatening and/or intervention needed
- CTCAE grade 5: resulting in death (fatal)

A similar table showing overall summary information of AEs during screening will be given.

In addition, frequency tables will summarize the number of subjects with injection site reactions.

Similar to 6.2, frequency tables will summarize the number of subjects with

- any event during Part A,
- any event during each 12-week Part B period
- any event during combination of these periods.

This will also include tabulation by dose actually received.

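### The treatment-emergent rule in SAP 6.4.1 looks only at the AE start date, so an event that begins in screening and worsens on BAY 1093884 can drop out of the treatment-emergent count

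*SAP*

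**What the plan says.** SAP 6.4.1 states that "AEs will be considered treatment-emergent if they begin after the first administration of study drug", with a limit of 30 days after the last administration. It adds: "Determination of whether or not an event is treatment-emergent will be derived after the missing or incomplete AE start date is imputed". The flag therefore depends on the start date, and SAP 4.3 supplies imputation rules for start dates only. The additional SAP of 10 March 2020 covers bleeding rates and plots and leaves this rule alone.

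AE collection begins before treatment. SAP 6.4.1 says: "The investigator has to record on the respective CRF pages all adverse events occurring in the period between the signing of the informed consent form". Collection then runs until follow-up closes. Protocol 9.2.1.1 allows the screening visit up to 6 weeks before Visit 2. The SAP also plans a separate screening summary: "A similar table showing overall summary information of AEs during screening will be given". It does not say how an AE is assigned to that table.

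Protocol 9.6.1.1, which separates medical history from adverse events, says: "Conditions that started or deteriorated after signing of informed consent will be documented as adverse events". The reference point there is consent, not the first dose.

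The primary variables in SAP 6.4 are "Incidences of drug-related AEs, SAEs, adverse events of special interest (AESIs), and clinically relevant abnormal laboratory values". In SAP 6.4.1, treatment-emergent AE is one of four items listed for the overall summary. The period tables count subjects with "any event during Part A", and likewise for each Part B period and for combinations.

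**The concern.** The protocol recognises deterioration as well as onset, but the SAP's flag recognises onset only. Suppose an AE begins at grade 1 during screening and reaches grade 3 after the first injections. If the site keeps it on one record with its pre-dose start date, the flag says it is not treatment-emergent, although the clinically important part happened on drug.

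Safety is the primary endpoint of an uncontrolled trial with 8 subjects planned per dose, so there is no comparator arm in which the same omission would occur and show its size. Where the worsening stays on the old record, the omission can only lower the treatment-emergent count. Without a stated recording rule, two sites could enter the same clinical course differently and obtain different flags.

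**Working it through.** The plan states no figure to reproduce: Protocol 10.4 and SAP 9.1 say that safety is descriptive and that no formal sample size was determined. The check has three parts.

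**1. The rule applied literally.** Flag = (start after first dose) and (start no later than last dose + 30 days). The window between consent and first dose can be 6 × 7 = 42 days. The test case is an AE with onset 10 days before first dose that worsens on day 14.

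| How the site records it | Start date used | Treatment-emergent under SAP 6.4.1 |
|---|---|---|
| One record, intensity updated | day −10 | No |
| Worsening entered as a new AE | day 14 | Yes |
| One record, rule with a worsening clause | day 14 (date of worsening) | Yes |

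The same clinical course gives opposite answers under the present rule, depending on a recording choice that neither document settles. A related detail is that SAP 4.3 can impute an incomplete start to the date and time of the first dose. That value fails a strict test of being after the first dose, although the imputation seems meant to bring the event in.

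**2. Which outputs are affected.**
- Treatment-emergent line of the overall summary (SAP 6.4.1): affected if the event stays on one record.
- Screening table and Part A/Part B tables, also by dose actually received (SAP 6.4.1): undefined. The text does not say whether an event counts by onset in the period or by being present in it.
- Drug-related AEs, SAEs and AESIs (SAP 6.4) and the SOC/PT tables (SAP 6.4.1): no restriction to treatment-emergent events is stated.
- DLTs and ad hoc DMC triggers (Protocol 9.6.1.6 and 9.6.1.7): neither refers to the flag.
- A condition present before consent that first deteriorates on drug becomes an AE under Protocol 9.6.1.1. The gap is confined to AEs with onset between consent and first dose.

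**3. Size.** With 8 subjects in a cohort, one affected subject changes the treatment-emergent proportion for a given preferred term by 1/8 = 12.5 percentage points. Exact (Clopper-Pearson) 90% intervals, the type the plan uses for its responder proportions, are:
- 0/8 = 0% (0 to 31.2%)
- 1/8 = 12.5% (0.6 to 47.1%)

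For the line counting subjects with any treatment-emergent AE, the shift is 12.5 points only if the subject has no other such event. As an assumption, take 0.5 to 2 AEs per subject per 12 weeks over 24 weeks, that is 1 to 4 expected, with Poisson counts. The chance of no other event is then e^−1 = 37% down to e^−4 = 2%, and the expected shift per affected subject is 4.6 down to 0.2 points.

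The documents give no rate for such cases. As an illustration only, let p be the assumed chance that a subject has a screening-onset AE that worsens on drug. The chance of at least one such subject is 1 − (1 − p)^n:

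| Assumed p | n = 8 | n = 24 |
|---|---|---|
| 2% | 15% | 38% |
| 5% | 34% | 71% |
| 10% | 57% | 92% |

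The finding does not rest on this table.

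**The case against.** The best defence is that Protocol 9.6.1.1 already covers the case. A deterioration on drug is a deterioration after consent, so it is documented as an AE; given its own post-dose start date, it is treatment-emergent under the SAP as written. That reading is possible, and under it no error arises. But the sentence separates medical history from AEs. It does not say that an event which is already an AE gets a second record when its grade rises. Other text fits a single evolving record at least as well: SAP 6.4.1 summarises maximum intensity, and Protocol 9.6.1.3.1 follows SAEs through updated reports. eCRF completion instructions might settle the matter, but they are not part of these documents.

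A reader might also infer more than the documents support:
- *That the worsened event will be reported as a screening event with its on-drug grade.* The SAP states neither how AEs reach the screening table nor which intensity is shown there.
- *That the primary endpoint is biased.* None of the primary variables is worded as treatment-emergent only. A worsening judged drug-related, or one that becomes serious, meets a primary variable whatever its flag. Laboratory worsening also appears as change from a pre-dose baseline (SAP 4.5.1 and 6.4.3).
- *That a dose-limiting worsening could escape notice.* The DLT and DMC rules do not use the flag.
- *That such an event is likely to occur.* Any probability depends on assumed rates. Six weeks is the maximum length of screening, many AEs may resolve before dosing, and bleeds are not recorded as AEs unless serious (Protocol 9.6.1).

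**Conclusion.** The concern holds in a limited form. The SAP's definition is based on onset alone, and no stated recording rule fills the gap. An AE that starts between consent and first dose and worsens on BAY 1093884 can therefore be missing from the treatment-emergent line, and its place in the period and dose tables is open. This rests on one condition that the documents leave unsettled: that the worsening is kept on the original record.

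The effect per affected subject is 12.5 percentage points for a given preferred term in a cohort of 8, and usually less for the line counting any treatment-emergent AE. How often this would happen cannot be derived from the documents. It is a defect in a stated rule with a clear remedy. It does not show that the primary variables or the safety oversight fail.

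**What to change.** Replace the definition in SAP 6.4.1 with wording to this effect: an AE is treatment-emergent if it begins, or if an event present before the first dose increases in CTCAE grade or becomes serious, at or after the first administration of study drug and not more than 30 days after the last. Saying *at or after* also keeps in the events that SAP 4.3 imputes to the first-dose time.

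Then:
- use the date of worsening as the onset when assigning such an event to a study part and dose;
- state in the SAP how AEs are assigned to the screening, Part A and Part B tables;
- instruct sites to open a new AE record when the grade of an existing AE rises after the first dose.

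The cost is a revised definition and a few lines on assignment in the SAP, plus one eCRF completion instruction. No treatment, visit or sample size changes. Treatment-emergent counts may be slightly less favourable.

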6.4.2 Vital signs

Vital signs (systolic and diastolic blood pressure, heart rate, respiratory rate and body temperature) obtained at Visit 1 (Screening), Visit 2 (before and 30-60 minutes after study drug administration), Visit 3, Visit 4, Visit 5, Visit 6 (before and 30-60 minutes after study drug administration), Visit 7 or any subsequent 12-week visit (before and 30-60 minutes after study drug administration) as well as during Final visit and Early termination visit will be displayed by means of descriptive statistics and change from baseline.

6.4.3 Laboratory parameter

Only centrally analyzed blood samples will be considered for analysis.

Central laboratory parameters at Visit 1 (Screening), Visit 2, Visit 3, Visit 4, Visit 5, Visit 6, Visit 7 or any subsequent 12-week visit as well as during Final visit and Early termination visit will be displayed by means of descriptive statistics and change from baseline.

High/low abnormalities and incidences of clinically relevant abnormal laboratory values by laboratory parameter will be presented, including various CBC, platelet, and serum chemistry parameters.

The values of antibodies against BAY 1093884 at Visit 2, Visit 3, Visit 4, Visit 5, Visit 6, each Visit 7 as well as during Final visit and Early termination visit will be displayed by means of descriptive statistics and change from baseline.

Incidences of binding and neutralizing antibodies against BAY 1093884 will be presented.

6.4.4 Subgroup analysis

An overall summary of number of subjects with drug-related AEs, SAEs and AESIs, incidences of clinically relevant abnormal laboratory and incidences of binding and neutralizing antibodies against BAY 1093884 will be given by the following subgroups:

- Type of hemophilia (hemophilia A, hemophilia B)
- Inhibitor status (with/without inhibitors)
- Previous treatment (on demand, on prophylaxis)

6.4.5 Pregnancies

Any reported pregnancy on any female participant will be displayed.

Any reported pregnancy occurring in partners of study subjects during the subject's participation in this study will be displayed.

7. Document history and changes in the planned statistical analysis

- First draft of SAP on 18-Jul-2018
- Final version of the SAP on 23-Jul-2018

8. References

9. Appendix

9.1 Determination of sample size

CCI [REDACTED] no formal determination of sample size was done.

Considering that this is a Phase 2 study for a rare disease, a sample size of 24 is a reasonable number to evaluate the safety of a multiple escalating dose of a new drug. Having the safety data of 8 subjects per cohort, a firm clinical understanding of the drug can be obtained (4 subjects per cohort have been evaluated for the single dose escalation in the first-in-man study). All safety parameters will be analyzed by descriptive statistics only, no hypothesis tests will be performed. The same holds true for the efficacy analysis. Therefore, no sample size calculation applies for this study

CCI [REDACTED]

Statistical Analysis Plan

Protocol No.: **BAY 1093884 / 19580**

Page: 19 of 19
